4.4. End of Study Definition

A participant is considered to have completed the study if they have completed all phases of the study, including the last visit or the last scheduled procedure shown in the [SoA](#).

The end of the study is defined as the date of the last visit of the last participant in the study or last scheduled procedure shown in the [SoA](#) for the last participant in the trial globally.

5. STUDY POPULATION

This study can fulfill its objectives only if appropriate participants are enrolled. The following eligibility criteria are designed to select participants for whom participation in the study is considered appropriate. All relevant medical and non-medical conditions should be taken into consideration when deciding whether a particular participant is suitable for this protocol.

Prospective approval of protocol deviations to recruitment and enrollment criteria, also known as protocol waivers or exemptions, is not permitted.

5.1. Inclusion Criteria

Participants are eligible to be included in the study only if all of the following criteria apply:

Age and Sex

1. Main cohort: Aged ≥ 2 years to <11 years (up to the day before 11th birthday inclusive) at time of enrollment; **CCI**

Type of Participant and Disease Characteristics

2. Documented, confirmed genetic diagnosis of achondroplasia from historical medical records prior to entry into this trial (test must have been performed at a laboratory fully accredited for genetic testing under local regulations).
3. Completed the C4181001 natural history study with at least 2 valid height/length measurements (at least 3 months apart) prior to enrollment in this study. One of these measurement timepoints must be within the 3 months prior to enrollment in C4181005.
4. Tanner stage 1 based on investigator assessment during physical examination (must include assessment of breast development for females, testicular stage for males).
5. Able to stand independently for height measurements (if ≥ 2 years of age at enrollment).

6. If aged <2 years at enrollment, has a documented historical MRI brain/cervical spine performed in the previous 12 months.

Informed Consent:

7. Capable of giving signed informed consent/assent as described in [Appendix 1](#), which includes compliance with the requirements and restrictions listed in the ICD and in this protocol.
8. Following receipt of oral and written information about the trial, the child (depending on local institutional review board/independent ethics committee requirements) must provide assent, and one or both (according to local regulations) parents or guardians of the child must provide signed informed consent before any trial-related activity is carried out.

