9.1. Estimands and Statistical Hypotheses

Height Growth Endpoint

Null hypothesis for height growth in this study is that height 12 months post-baseline for children on recifercept is equal to the expected height growth for the achondroplasia reference population based on Merker (2018).³⁰ The alternative hypothesis is that height growth for recifercept-treated participant is greater than the expected growth for achondroplasia reference population based on Merker (2018).³⁰

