9.2. Sample Size Determination

Sample size determination is based on the co-primary endpoint of height growth, defined as change from baseline of height at 12 months for participants on drug versus change from baseline of height at 12 months for a reference achondroplasia population. A total of 54 participants randomized to three dose levels in order to obtain 15 participants per dose, assuming a one-sided family-wise error rate of 0.05 with a Bonferroni correction (0.017 after Bonferroni adjustment for 3 comparisons), and inter-participant variability of .15 (estimated from C4181001), there is over 90% power to detect at least one dose providing 50% height growth above reference. No statistical comparison will be made between recifercept doses.

PK Study Cohort:

No formal sample size calculation was performed and 12 participants will be selected empirically to characterize PK, safety and tolerability after single 3 mg/kg dose administration of two formulations.

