6. ANALYSES AND SUMMARIES

6.1. Primary Endpoint(s)

6.1.1. Increase in height growth above expected in reference population

6.1.1.1. Main Analysis

- Estimand strategy: Hypothetical ([Section 2.1.1](#)).
- Analysis set: FAS ([Section 4](#)).
- Analysis methodology: Change from baseline relative to Merker (2018) will be analyzed using MMRM including data from Months 3, 6, 9, and 12 with gender (and possibly age) as a covariate, subject (and/or time) as a random effect and an unstructured covariance matrix ([Section 5.2.1](#)).
- Intercurrent events and missing data: Data after study drug discontinuation and rescue will be excluded; intermediate missing values will not be imputed.
- The sample size, mean, standard deviation, median, minimum, and maximum at the baseline and postbaseline visits for observed standing height and change from baseline will be presented for each treatment arm.
- The least-squares (LS) means, the 95% confidence interval for the LS means, the difference between the LS means for each pair of treatment groups, and the corresponding 95% confidence interval will be presented for change from baseline in standing height for all postbaseline visits.

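### Every child brings pre-treatment heights from C4181001, but the visible primary and sensitivity analyses test growth only against a published reference; a supportive within-child comparison would check that assumption cheaply.

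*Protocol*

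**What the plan says.** **Pre-treatment data.** Protocol 5.1, criterion 3, admits a child only if the child has "Completed the C4181001 natural history study with at least 2 valid height/length measurements (at least 3 months apart) prior to enrollment in this study". It adds: "One of these measurement timepoints must be within the 3 months prior to enrollment in C4181005".

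**Test.** Under the null hypothesis in Protocol 9.1, growth on recifercept "is equal to the expected height growth for the achondroplasia reference population". SAP 5.1 says the same. The variable is observed change in standing height divided by the change expected from the reference (SAP 2.1.1 and Appendix 2.2, where it is called H), so the null value is 1.

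**Models.** Protocol 9.4.2 plans an ANOVA with dose terms. SAP 6.1.1.1 plans an "MMRM including data from Months 3, 6, 9, and 12 with gender (and possibly age) as a covariate", and the Appendix 4 code has dose, month, gender and age. None of these contains a pre-treatment growth term. The sensitivity analysis (SAP 6.1.1.2 and Appendix 1) changes the analysis set to the PPAS and keeps the same reference.

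**Where C4181001 is used.** Protocol 9.2 takes its SD from it: "inter-participant variability of .15 (estimated from C4181001". SAP 3.4 falls back on it when a baseline value is missing.

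**Comparators.** All three arms are active (Protocol 4.1), and Protocol 9.2 rules out statistical comparison between doses.

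**The concern.** Without a control arm, the test against 1 is a test of drug effect only if these children, untreated, would average a ratio of 1. The documents do not show that they would. The cohort is selected: Tanner stage 1, 7 to 30 kg, no severe obesity, no growth-affecting treatment and no recent bone surgery (Protocol 5.1 and 5.2). It is measured by trained anthropometrists with standardised equipment (Protocol 6.3.2). The reference is a published European cohort.

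The small assumed SD makes the test sensitive to small departures from 1, whatever their cause. An upward offset would be read as efficacy and a downward one would mask it. Repeating the analysis in the PPAS leaves any offset in place. The sponsor already holds data on each child that could show whether an offset exists.

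**Working it through.** **Inputs from Protocol 9.2**
- Size: "A total of 54 participants randomized to three dose levels in order to obtain 15 participants per dose", so n = 15 per dose.
- Error rate: "assuming a one-sided family-wise error rate of 0.05 with a Bonferroni correction (0.017 after Bonferroni adjustment for 3 comparisons", so α = 0.05/3.
- SD = 0.15, read as the SD of the observed/expected ratio; the protocol does not state the scale.
- Effect: ratio 1.5 against 1, so δ = 0.50.

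**The plan's own figure.** The claim is "there is over 90% power to detect at least one dose providing 50% height growth above reference". For a one-sample one-sided t-test, SE = 0.15/√15 = 0.0387 and the noncentrality is 0.50/0.0387 = 12.9. Power exceeds 99.99% per dose, so the stated floor is met.

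**Smallest significant mean.** t(0.9833; 14 df) = 2.36, and 2.36 × 0.0387 = 0.091. A mean ratio of about 1.09 is significant.

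**False positives under an offset b, no drug effect.** Per-dose rate p = P[T(14 df, noncentrality b√15/SD) > 2.36]. For at least one dose, 1 − (1 − p)³, with the same fixed offset in each arm. The values of b, and the SD of 0.30, are assumptions.

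| SD | Offset | Noncentrality | Per dose | At least one dose |
|---|---|---|---|---|
| 0.15 | 0 | 0 | 1.7% | 4.9% |
| 0.15 | 5% | 1.29 | 17% | 44% |
| 0.15 | 10% | 2.58 | 60% | 93% |
| 0.30 | 5% | 0.65 | 6% | 18% |
| 0.30 | 10% | 1.29 | 17% | 44% |

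**Within-child difference.** Take D = on-treatment H minus the same child's pre-treatment ratio. An offset that is stable across the two periods cancels, so the rate returns to 1.7% per dose. The price is variance: SD(D) = √(0.15² + s²), where s is the run-in SD (not in the documents) and the two ratios are taken as independent.

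| s | SD(D) | Power, +50% | Power, +25% |
|---|---|---|---|
| 0.30 | 0.335 | 99.9% | 70% |
| 0.45 | 0.474 | 95% | 40% |
| 0.50 | 0.522 | 89.8% | 34% |
| 0.60 | 0.618 | 77% | 25% |

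The value 0.60 is a pessimistic case. If the 0.15 were all measurement error on a 12-month change, a 3-month run-in has about a quarter of the expected growth, giving 4 × 0.15 = 0.60.

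**Covariate instead of difference.** With correlation ρ between the two ratios, adjusting to a pre-treatment ratio of 1 removes on average the fraction ρ × 0.15/s of an offset. For ρ = 0.3 to 0.5 and s = 0.30 to 0.45 (assumed) that is 10% (0.3 × 0.15/0.45) to 25% (0.5 × 0.15/0.30). In a simulation of three arms of 15 with a common slope and a 10% offset, about 50% to 60% false positives per dose remained, against about 65% without the covariate when the residual variance is likewise pooled. The LS-means statement in SAP Appendix 4 evaluates covariates at their sample mean. Done that way, none of the offset is removed while the SE shrinks, and the rate is about 68% to 77%.

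**The case against.** **The offset is hypothetical.** This stands. Neither its size nor its direction is in the documents. The table shows sensitivity, not an expected error rate, and a reader should not infer that a positive result would be false.

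**A 5% to 10% offset could not pass for the planned effect.** This stands in part. A mean near 1.05 to 1.10 is far from the +50% in Protocol 9.1.1, and a success rule set there would rarely be met by an offset alone. But Protocol 9.1 and SAP 5.1 test equality with the reference. These passages should be reconciled.

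**Inference does not rest wholly on the reference.** This stands in part. Doses are randomised over a wide range, and SAP 6.1.1.1 reports pairwise LS-mean differences with confidence intervals, in which a shared offset essentially cancels. These are estimates without a formal test in the protocol, and they show differences between doses, not the effect of a dose against no treatment.

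**Run-in growth is too noisy.** This stands as a limit on the role of the analysis. Three months is the permitted minimum, and for +25% power is modest throughout the range. Criterion 3 also accepts length as well as height. Protocol 8.1.1 measures length below age 2, so a child enrolled soon after age 2 may have a run-in that mixes methods. Neither document says why run-in growth was left out, so noise cannot be given as the sponsor's reason.

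**Redaction.** Some endpoint and analysis text is blacked out. Absence can be stated only for the visible text.

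**Conclusion.** The point holds as a supportive-analysis gap. In the visible text, the main efficacy test depends on an untested assumption that the untreated cohort matches the reference, and data already required of every child could check it. At SD 0.15 and 15 per dose, an assumed 5% or 10% upward offset gives 17% or 60% false positives per dose. At SD 0.30 it gives 6% or 17%.

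Two stronger readings are tempting and are not supported. One is that C4181001 is ignored altogether: it supplies the SD and the fallback baselines. The other is that adding pre-treatment growth as a covariate would cure the problem: it removes a small part of an offset when evaluated at 1, none at the sample mean, and at most adds precision.

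The conclusion assumes that 0.15 is the SD of the ratio and that the test is against 1. Cancellation within child assumes that the offset is stable between run-in and treatment.

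**What to change.** In the SAP:
- Define each child's pre-treatment ratio as observed over expected growth across the longest available C4181001 interval. State how expected change is obtained for intervals that do not match the 6-month steps of SAP Appendix 2.2.
- Report its mean and confidence interval by dose and overall, as a direct check of the reference assumption.
- Add the within-child change (on-treatment H minus pre-treatment ratio) by dose as a supportive analysis, with a rule for minimum interval or weighting by interval length.
- State how children whose run-in mixes length and standing height are handled, for example by excluding the mixed interval or by a sensitivity analysis.
- If the ratio is also entered as a covariate, describe this as a precision measure only.

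The cost is SAP wording and linkage to a study that every participant has completed; no new visits or participants are needed. The downside is lower precision, so the primary test stays as it is.

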5.2. Exclusion Criteria

Participants are excluded from the study if any of the following criteria apply:

Medical Conditions:

1. Presence of co-morbid conditions or circumstances that, in the opinion of the investigator, would affect interpretation of growth data or ability to complete the trial procedures.
2. Other medical or psychiatric condition including recent (within the past year) or active suicidal ideation/behavior or laboratory abnormality that may increase the risk of study participation or, in the investigator's judgment, make the participant inappropriate for the study.
3. Presence of severe obesity (BMI >95th percentile on Hoover-Fong BMI charts) [Hoover-Fong et al, 2008].¹⁴
4. Known closure of long bone growth plates (cessation of height growth).
5. Body weight <7 kg or >30 kg.
6. Moderate or severe renal impairment CrCL GFR <60 mL/min/1.73m² (Calculated GFR based on updated "bedside" Schwartz formula for pediatric patients (CrCL (mL/min/1.73 m²) = 0.413 * Height (cms)/ Serum cr (mg/dL) or hepatic impairment (AST/ALT >1.5 ULN).
7. History of hypersensitivity to study intervention or any excipients.

Prior/Concomitant Therapy:

8. History of any prior treatment with human growth hormone or related products (including insulin-like growth factor 1 [IGF-1]).

9. History of receipt of any treatment that are known to potentially affect growth (including oral steroids >5 days in the last 6 months, high dose inhaled corticosteroids (>800 mcg/day beclametasone equivalent) and medication for attention deficit hyperactivity disorder).
10. History of limb lengthening surgery (defined as distraction osteogenesis/Illizarov/callostasis technique following submetaphyseal osteotomy to extend bone length).
11. Any limb lengthening/corrective orthopaedic surgery planned at any point during the trial period.
12. Less than 6 months since fracture or surgical procedure of any bone determined from the screening visit date.
13. Presence of any internal guided growth plates/devices.
14. History of removal of internal guided growth plates/devices within less than 6 months.
15. History of receipt of any investigational product for achondroplasia or that may affect growth/interpretation of growth parameters.
16. History of receipt of an investigational product (not for achondroplasia/growth affecting) within the last 30 days or 5 half-lives (whichever is longer).

Other Exclusions

17. Investigator site staff or Pfizer employees directly involved in the conduct of the study, site staff otherwise supervised by the investigator, and their respective family members.

5.3. Lifestyle Considerations

5.3.1. Contraception

Should a participant become a WOCBP (defined as reaching menarche) during the course of the study then the investigator or his or her designee, in consultation with the participant and their guardian, will confirm that the participant has been informed of the potential risks of pregnancy whilst receiving study intervention and advised of the need for continuing total abstinence from sexual activity. At time points indicated in the [SoA](#), the investigator or designee will inform the participant of the need to use continue total abstinence from sexual activity and document the conversation and the participants affirmation in the participants' chart. This also applies to males should they become sexually active. In addition, the investigator or designee will instruct the participant or guardian to call immediately if total abstinence from sexual activity is discontinued or if pregnancy is known or suspected in the participant or partner.

5.4. Screen Failures

Screen failures are defined as participants who consent to participate in the clinical study but are not subsequently randomly assigned to study intervention. A minimal set of screen failure information is required to ensure transparent reporting of screen failure participants to meet the CONSORT publishing requirements and to respond to queries from regulatory authorities. Minimal information includes demography, screen failure details, eligibility criteria, and any SAE.

Individuals who do not meet the criteria for participation in this study (screen failure) may be rescreened.

6. STUDY INTERVENTION

Study intervention is defined as any investigational intervention(s), marketed product(s), placebo, medical device(s), or study procedure(s) intended to be administered to a study participant according to the study protocol.

For the purposes of this protocol, study intervention refers to reciferecept (PF-07256472) provided as lyophilized powder for solution for injection/infusion, 50 mg/vial.

Further details for the sections below can be found in the Investigational Product Manual (IP Manual) and/or dosing diary.

6.1. Study Intervention(s) Administered

Intervention Name	PF07256472 (Reciferecept).
ARM Name (group of patients receiving a specific treatment (or no treatment)	Refer to the study schema provided in the STUDY DESIGN section.
Type	Biologic.
Dose Formulation	Lyophilized powder for solution for injection.
Unit Dose Strength(s)	50 mg/vial.
Dosage Level(s)	Refer to the study schema provided in the STUDY DESIGN section.
Route of Administration	Subcutaneous injection.
Use	Experimental.
IMP or NIMP	IMP.
Sourcing	Provided centrally by the sponsor. Refer to the IP Manual for further information.
Packaging and Labeling	Study intervention will be provided in vials. Each vial will be labeled as required per country requirement. The IP will be provided as open label, as the only personnel required to be blinded are anthropometrists. Vials are single-use only.
Current/Former Name(s) or Alias(es)	TA-46.

6.1.1. Administration

Administer study intervention according to the Subcutaneous Dosing Instructions (see [Appendix 10](#)). Study intervention should not be self-administered by the participant.

6.2. Preparation/Handling/Storage/Accountability

- The investigator or designee must confirm appropriate temperature conditions have been maintained during transit for all study interventions received and any discrepancies are reported and resolved before use of the study intervention.
- Only participants enrolled in the study may receive study intervention and only authorized site staff may supply study intervention. Authorized site staff and caregivers, who have demonstrated their proficiency, may prepare and administer study intervention.
- All study interventions stored at the clinical site must be stored in a secure, environmentally controlled, and monitored (manual or automated recording) area in accordance with the labeled storage conditions with access limited to the investigator and authorized site staff. At a minimum, daily minimum and maximum temperatures for all site storage locations must be documented and available upon request. Data for nonworking days must indicate the minimum and maximum temperatures since previously documented for all site storage locations upon return to business.
- Site staff will instruct caregivers on the proper storage requirements for take home study intervention.
- All study interventions stored at participants' homes must be stored according to the labeled storage conditions.
- Any excursions from the study intervention label storage conditions should be reported to Pfizer upon discovery along with any actions taken.
 - The site should actively pursue options for returning the study intervention to the storage conditions described in the labeling, as soon as possible. Once an excursion is identified, the study intervention must be quarantined and not used until Pfizer provides permission to use the study intervention. Specific details regarding the definition of an excursion and information the site should report for each excursion will be provided to the site in the IP Manual.
 - Pfizer cannot analyze the acceptability of any excursion that occurs once the study intervention leaves the clinical site. If an excursion occurs at the participants' homes, the caregivers must quarantine the study intervention until it can be returned to the clinical site for accountability. Further instructions are provided in the dosing diary.
- Any storage conditions stated in the SRSD will be superseded by the storage conditions stated on the label.

- Study interventions should be stored in their original containers.
- See the IP manual for storage conditions of the study intervention once reconstituted.
- Details of the transport to and storage of study intervention at the participants' homes can be found in the dosing diary.
- Used and unused vials stored at the participants' homes must be returned to site.
- The investigator, institution, or the head of the medical institution (where applicable) is responsible for study intervention accountability, reconciliation, and record maintenance (ie, receipt, reconciliation, and final disposition records), such as the IPAL or sponsor-approved equivalent and dosing diary. All study interventions will be accounted for using a study intervention accountability form/record.
- Further guidance and information for the final disposition of unused study interventions are provided in the IP Manual. All destruction must be adequately documented. If destruction is authorized to take place at the investigator site, the investigator must ensure that the materials are destroyed in compliance with applicable environmental regulations, institutional policy, and any special instructions provided by Pfizer.

Upon identification of a product complaint, notify the sponsor within 1 business day of discovery, as described in the IP Manual.

6.2.1. Preparation and Dispensing

Study intervention should be prepared and dispensed by an appropriately qualified and experienced member of the study staff (eg, physician, nurse, physician's assistant, nurse practitioner, pharmacy assistant/technician, or pharmacist) as allowed by local, state, and institutional guidance. Site staff will reference the IP Manual for instructions on how to prepare the study intervention for administration. A second staff member will verify the preparation of the dose. All persons who are responsible for dose preparation and dispensing of IP must be listed on the Delegation of Authority log.

Caregivers will reference the Dosing Instructions Diary for instructions on how to prepare and administer the study intervention at home, following demonstration of their proficiency at the site.

Adequate caregiver competency for home-dosing may include, but not be limited to the following criterion:

- Caregivers demonstrate adequate adherence to storage & preparation routine including sterile technique.
- Caregivers understand which sites can be used for injection and the need to rotate these sites.

- Caregivers demonstrate correct techniques to reconstitute & draw up solution into syringe for administration.
- Caregivers demonstrate correct injection technique including preparation of skin prior to injection.
- Caregivers show knowledge of adequate disposal of used medication supplies and completion of dosing diary.

The caregiver should be instructed to maintain the study intervention in the vials and cartons provided, throughout the course of dosing, and return the vials, in the cartons provided, to the site at the next study visit.

